Describe the characteristics of the subject population, including age range, gender, ethnic background and health status. Identify the criteria for inclusion and exclusion.

Provide the following information:

- A description of the subject selection criteria and rationale for selection in terms of the scientific objectives and proposed study design;
- A compelling rationale for proposed exclusion of any sex/gender or racial/ethnic group;
- Justification for the inclusion of vulnerable groups such as children, prisoners, adults with impaired consent capacity, or others who may be vulnerable to coercion or undue influence.

Please consider these resources:

[NIH Diversity Policy](#)

[FDA Diversity Guidance](#)

For the prospective section, based on the effect sizes of the mandibular advancement device (MAD) based on past meta-analyses, we conducted a GPower which revealed that obtaining a sample size of 45 participants would provide us 80% power to detect the anticipated effects. To compensate for dropout/attrition, we aim to recruit 50 participants.

No specific population will be targeted in terms of sex/gender or racial/ethnic background. The age range considers patients between 18 and 80 y.o. with a diagnosis of obstructive sleep apnea (OSA). Participants will be recruited from the consecutive patients referred to the Orofacial Pain Clinic for the management of OSA with a MAD.

Inclusion criteria:

- Age: >18 and <80 years old.
- No history of previous use of a MAD.
- Diagnosis of OSA by a sleep physician based on a PSG or HSAT (done >12 months before - evaluation date or > 12 months with >10% variation of BMI).
- Upon clinical examination: >8 teeth per arch; range of anteroposterior mandibular mobility >5 mm.
- Informed consent to participate in the study.

Exclusion criteria:

- Patients with concomitant diagnosed sleep disorders (i.e. insomnia, narcolepsy, restless legs syndrome, rapid eye movement sleep behavior disorder).
- History of previous allergic reaction to the appliance material (Polyamide 12).
- Patients using combination therapy for the management of OSA (i.e. PAP therapy or positional therapy).
- Upon clinical examination: periodontal disease (>4 mm on periodontal probing, with bleeding on probing, visual signs of periodontal inflammation); tooth horizontal mobility >1 mm, vertical mobility, and unfavorable crown to root ratio; open cavities, loose or fractured restorations, or patient undergoing restorative dental treatments.

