- Use one of the attachment buttons in this section or under the Additional Information section to include supplemental information with your application. During the document upload process, you will be able to provide a brief description of the attachment.

Background

Include a brief review of existing literature in the area of your research. You should identify gaps in knowledge that should be addressed and explain how your research will address those gaps or contribute to existing knowledge in this area. For interventional research, search PubMed and ClinicalTrials.gov for duplicative ongoing and completed trials with same condition and intervention(s).

Multiple mandibular advancement devices (MAD) are available on the market and have been used for the management of obstructive sleep apnea (OSA). They are specifically used to prevent upper airway collapse by protruding the mandible forward, thus altering the jaw and tongue position. The models vary regarding the titrability and the level of customization [1]. Titratable devices are thought to increase treatment success by allowing gradual adaptation to optimal protrusion [2] [3]. The effective degree of mandibular protrusion used in published studies has been highly variable, ranging from 50% to 80% of maximal protrusion [1] [4] [5] [6]. In mild to moderate cases of OSA, no differences were found between 50% and 75% of protrusion [5], whereas in severe cases of OSA, 75% of protrusion demonstrated to be more efficacious than 50% [6].

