- *Research Repositories*: If the purpose of this submission is to establish a Research Repository (bank, registry) and the material you plan to collect is already available from a commercial supplier, clinical lab, or established IRB approved research repository, provide scientific justification for establishing an additional repository collecting duplicate material. Describe the repository design and operating procedures. For relevant information to include, see the [UK Research Biospecimen Bank Guidance](#) or the [UK Research Registry Guidance](#).

This study will incorporate a prospective and a retrospective section:

The prospective study will be an uncontrolled open-label clinical trial.

The retrospective component will extract previously collected archival data from medical records of patients that started MAD therapy for OSA at the Orofacial Pain Clinic (Kentucky Clinic). These subjects had a second sleep study performed to assess the effectiveness of the mandibular advancement devices.

Attachments

Subject Recruitment Methods & Advertising

Describe how the study team will identify and recruit subjects. Please consider the following items and provide additional information as needed so that the IRB can follow each step of the recruitment process.

- How will the study team identify potential participants?
- Who will first contact the potential subjects, and how?
- Will you use advertisements? If so, how will you distribute those?
- How and where will the research team meet with potential participants?
- If applicable, describe proposed outreach programs for recruiting women, minorities, or disparate populations.
- How will minimize undue influence in recruitment?
- Attach copies of all recruiting and advertising materials (emails, verbal scripts, flyers, posts, messages, etc.).

For additional information on recruiting and advertising:

- [IRB Application Instructions - Advertisements](#)
- [PI Guide to Identification and Recruitment of Human Subjects for Research](#)

PROSPECTIVE SECTION:

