At the device delivery appointment, we will fabricate an aligner for the patient to wear for 10 minutes each morning after waking and removing the OrthoApnea NOA® oral appliance. The morning aligner (TAP® AM Aligner) is a record of the patient's habitual bite (the way the teeth come together normally) that will reposition their mandible back into its normal position. It is part of the standard of care for patients undergoing mandibular advancement (MAD) therapy. The aligner is constructed from a thermoplastic material that, when heated, can be molded by hand onto the upper or lower teeth. Once the thermoplastic material is molded around the teeth, they will be instructed to bite down while it is still soft. This will create indentations for the opposing teeth and allow them to be set at their 'normal' and proper biting position. After the molded thermoplastic material has hardened at normal temperature, it is removed from the mouth and trimmed, if needed.

Follow up sessions will be scheduled every two weeks until maximum therapeutic benefit is achieved. At each follow up visit patients will be asked to fill out a questionnaire and further advancement of the MAD will be determined by changes in patients' symptoms and Epworth Sleepiness Scale (ESS). Measures of successful management include: ESS < 10, and >70% reduction or absence of snoring, observed apneic events, and daytime fatigue, to be assessed via questionnaire using a numerical rating scale (NRS). Once the patient has obtained successful management of symptoms, 80% of maximum protrusive or is unable to tolerate the advancement, a home sleep apnea test (Alice NightOne, Phillips Respironics®) will be provided to the patient to perform one night while wearing the appliance to determine the efficacy of the MAD. We will verbally instruct the patient how to operate the machine, and a printed copy of the manufacturer protocol for patients will be provided. Additionally, we will provide our contact number if any question arise. An appointment will be scheduled in the following 2-3 days to return the machine, and to further advance the appliance if needed. Sleep parameters including: AHI, RDI, minimum and average oxygen saturation will be extracted from the initial PSG, and by a trained technician from the final home sleep apnea test, which will be scored following the American Academy of Sleep Medicine Scoring Manual.

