The efficacy of the appliance for the management of OSA will be established based on two criteria. Criterion I: > 50% reduction of AHI/RDI. Criterion II: AHI/RDI < 5 events/hour or <15 events/hour with a significant reduction of OSA associates symptoms as defined before. Therapeutic failure will be established when at 100% of advancement of the device, there is less than 50% of reduction of the AHI/RDI with a residual AHI/RDI >5 events/hour with OSA associates symptoms.

If the criteria for success is reached, the participation of the patient in the present study will be ended. The subject will be offered to continue with standard of care in the OFPC for future follow-ups, and a report will be provided and sent to the treating sleep physician. The subject will be allowed to keep the appliance after the study is completed. If participants do not reach a successful management of OSA at 100% of advancement, they will be referred back to their referring sleep physician to consider another treatment option.

The participation in this research will last between seven to sixteen weeks depending on the time for each patient's individual improvement. The initial visit will last 45-60 minutes, and the follow-up sessions will take about 30-45 minutes. After participation in the study is completed, the participants will be allowed to keep the MAD and all the accessories provided by the manufacturer

RETROSPECTIVE SECTION:

Archival data will be extracted from records of patients that started MAD therapy for OSA at the Orofacial Pain Clinic (University of Kentucky) between 01/01/2010 and 08/17/2021. An active study involving MAD therapy outcomes (protocol #46643; same PI, [name] [name]) includes a consent form for the retrospective participants to collect retrospective data and future use of that data in future research projects. The data collection process of the previous study is being conducted using RED Cap (CCTS - University of Kentucky), and through that software, we intend to obtain a report to identify subjects that started MAD therapy and had a second sleep study performed to assess the effectiveness of the MAD. Data regarding demographic characteristics (age, gender, BMI and OSA

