diagnosis), sleep parameters (AHI, RDI, minimum and average oxygen saturation), level of advancement of the MAD (%) prior to the second sleep study, and compliance of use will be extracted creating a deidentified "report" (spreadsheet) from the RED Cap database (assigning progressive numbers (starting with M51)).

Attachments

Data Collection & Research Materials

In this section, please provide the following:

- Describe all sources or methods for obtaining research materials about or from living individuals (such as specimens, records, surveys, interviews, participant observation, etc.), and explain why this information is needed to conduct the study.
- For each source or method described, please list or attach all data to be collected (such as genetic information, interview scripts, survey tools, data collection forms for existing data, etc.).
- If you will conduct a record or chart review, list the beginning and end dates of the records you will view.

This study has a prospective and a retrospective component. (SEE ANNEX IN ATTACHMENTS)

1) Prospective study: data will be obtained using paper questionnaires:

- Demographic information regarding age, race, gender and comorbidities will be extracted from the initial questionnaire (Annex 1).
- The self-reported use of MAD will be assessed at each follow-up via questionnaire on a five-point checklist (number hours per night and nights per week) (to be extracted from Annex 6).
- Epworth sleepiness scale (ESS) (Annex 1 and 6)
- Snoring, observed apneic events, and daytime fatigue, to be assessed via questionnaire using a numerical rating scale (NRS) (to be extracted from Annex 1 and 6).
- Sleep parameters including: AHI, RDI, minimum and average oxygen saturation will be extracted from the initial PSG, and by a trained technician from the final home sleep apnea test.
- The presence of signs, symptoms of TMD will be assessed following the Diagnostic Criteria for Temporomandibular Disorders (DC/TMD) Symptom Questionnaire and Examination Form (Annex 2 and 4).

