BENEFITS vs. RISKS: This therapeutic option can be associated with minimal and non life-threatening risks, and the risks to subjects are reasonable in relation to the anticipated benefits. The mandibular advancement devices are considered as a standard care option for the management of OSA.

Available Alternative Opportunities/Treatments

Describe alternative treatments or opportunities that might be available to those who choose not to participate in the study, and which offer the subject equal or greater advantages. If applicable, this should include a discussion of the current standard of care treatment(s).

Continuous positive air pressure (CPAP) is the main therapeutic option in patients with OSA. Reduced symptoms of sleepiness improved health-related quality of life, cardiovascular outcomes such as hypertension, dyslipidemia, and insulin resistance after CPAP treatment have been reported. In the last few decades, the clinical use of oral appliances for the management of snoring and obstructive sleep apnea has markedly increased. When comparing CPAP versus mandibular advancement devices (MAD), there was found to be no significant difference between MAD and CPAP in the percentage of mild OSA patients achieving their target AHI/RDI/ REI after treatment. However, for patients with moderate to severe OSA the odds of achieving the target AHI were significantly greater with CPAP than with MAD.

The patients referred to the Orofacial Pain Clinic for MAD therapy, the ones that will be targeted to be recruited for this study, are patients that were not able to tolerate previous therapeutic options.

[Back to Top](#)

Records, Privacy, and Confidentiality

Specify where the data and/or specimens will be stored and how the researcher will ensure the privacy and confidentiality of both. Specify who will have access to the data/specimens and why they need access.

Describe how data will be managed after the study is complete:

- If data/specimens will be maintained, specify whether identifiers will be removed from the maintained information/material.
- If identifiers will not be removed, provide justification for retaining them and describe how you will protect confidentiality.
- If the data/specimens will be destroyed, verify that this will not violate [retention policies](#) and will adhere to applicable facility requirements.

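### Criterion II has no baseline term, so a participant entering with AHI/RDI 5-14 can count as an efficacy success with no fall in AHI

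*Combined protocol and SAP*

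**What the plan says.** Research Procedures gives two efficacy criteria. Criterion I is a fall of more than 50% in AHI/RDI. Criterion II is "AHI/RDI < 5 events/hour or <15 events/hour with a significant reduction of OSA associates symptoms as defined before". The symptom standard it refers back to is in the same section: "Measures of successful management include: ESS < 10, and >70% reduction or absence of snoring, observed apneic events, and daytime fatigue", rated by the patient on questionnaire scales. The efficacy test is one night of home recording with the appliance in place.

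The inclusion criteria ask for "Diagnosis of OSA by a sleep physician based on a PSG or HSAT" and give no AHI/RDI minimum. The documents treat mild disease as within the use of these devices. The Background says "In mild to moderate cases of OSA, no differences were found between 50% and 75% of protrusion", and the section on alternative treatments reports "no significant difference between MAD and CPAP in the percentage of mild OSA patients achieving their target AHI/RDI/ REI after treatment".

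Under Study Design, "The prospective study will be an uncontrolled open-label clinical trial". The STATISTICAL METHODS text (Aim 1.1) calculates a success proportion separately for each criterion. Aim 1.2 then describes the advancement needed among those who succeeded, without naming the criterion. The same paragraph plans paired t-tests of the measured parameters before and after treatment.

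**The concern.** A threshold on the follow-up value shows a treatment effect only if participants start on the wrong side of it. For anyone entering with AHI/RDI of 5-14, the below-15 part of Criterion II is satisfied before the appliance is fitted. What is left is that one follow-up night stays below 15 and that the symptom rule is met. Without a control group or blinding, reported symptoms can improve for reasons other than a change in sleep-disordered breathing.

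For this subgroup, the Criterion II proportion cannot be read as efficacy on sleep apnea, yet Research Procedures uses it to establish efficacy. There may also be an effect on Aim 1.2. If Criterion II defines success there, a low-baseline participant whose symptoms settle at the starting 50% protrusion could be recorded as efficacy at 50% with no change in AHI. Needing less advancement is the property that the Background attributes to this device.

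**Working it through.** **Step 1. Apply the rules as written.** Let b be baseline AHI/RDI, f the follow-up value, and S whether the symptom rule is met.

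- Criterion I: (b − f)/b > 0.5
- Criterion II: f < 5, or (f < 15 and S)
- Therapeutic failure (at 100% advancement): fall below 50%, and f > 5, and residual symptoms

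| b to f | S met | Criterion I | Criterion II | Failure rule |
|---|---|---|---|---|
| 8 to 8 | yes | no | **yes** | no |
| 10 to 10 | yes | no | **yes** | no |
| 14 to 14 | yes | no | **yes** | no |
| 8 to 14 | yes | no | **yes** | no |
| 10 to 10 | no | no | no | yes |
| 15 to 15 | yes | no | no | no |
| 30 to 30 | yes | no | no | no |
| 16 to 14.9 | yes | no | **yes** | no |

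An unchanged AHI can pass only when baseline is below 15, and only with the symptom rule met. The failure rule does not catch these cases because it requires residual symptoms. The last row shows that a small fall from just above 15 also passes.

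**Step 2. Look for a correction elsewhere in the plan.** Criterion I is reported beside Criterion II and does not gate it. The paired t-tests describe group means. They do not identify which Criterion II successes had no fall, and because they stand in the Aim 1.2 paragraph they may cover only successes. The planned exploratory comparison of successes and failures concerns baseline demographics. No stratification by baseline AHI/RDI is stated.

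**Step 3. Illustrate the size.** The plan has no figure of its own to reproduce. It gives neither the baseline mix, nor the night-to-night variation, nor the symptom response, so all of these are assumptions. Assume no true effect on AHI, baseline uniform on 5-15, and f = b × exp(e) with e normal, mean 0, SD s.

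| s | P(f < 15) | P(f < 5) | P(5 ≤ f < 15) | P(b ≤ f < 15) | Share of the 5 ≤ f < 15 group meeting Criterion I |
|---|---|---|---|---|---|
| 0.2 | 0.894 | 0.045 | 0.848 | 0.394 | 0.000 |
| 0.3 | 0.850 | 0.073 | 0.776 | 0.350 | 0.005 |
| 0.4 | 0.810 | 0.104 | 0.706 | 0.310 | 0.019 |
| 0.5 | 0.775 | 0.137 | 0.638 | 0.275 | 0.035 |

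Success through the below-15 limb alone is P(5 ≤ f < 15) × symptom response. Take symptom response as 30% to 70%, independent of f:

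- lowest: 0.638 × 0.3 = 0.19
- highest: 0.848 × 0.7 = 0.59

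Multiply by the share of all 50 participants with baseline 5-14:

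- 20%: 0.04 to 0.12 of all participants (1.9 to 5.9 people)
- 40%: 0.08 to 0.24 (3.8 to 11.9)
- 60%: 0.11 to 0.36 (5.7 to 17.8)

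**Step 4. Check above 15.** Under the same model, P(f < 15) is 0.091 to 0.236 for baseline uniform on 15-30 and 0.244 to 0.383 for 15-20. The problem is largest below 15 but does not stop there.

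**The case against.** The best defence is that Criterion II is a treatment target. A residual-level rule ignores baseline by design, Criterion I supplies the relative response, and AHI change is also tested directly. The documents name no primary endpoint, so efficacy does not rest on Criterion II alone. This stands as a reason to keep the criterion. It does not make the Criterion II proportion interpretable for participants who began below 15.

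A reader might infer that any self-reported improvement is enough. The documents do not support that. The symptom rule is demanding, and a measured test below 15 is still required. The annexes are not in the text, so whether a bed partner contributes to the rating of observed apneas is unknown. A rise from 8 to 14 with all symptoms resolved is allowed by the rule, but nothing shows that it would be common. The rule still has limits as a safeguard. Meeting it is one of the triggers for the home test, so participants tested by that route have met it beforehand.

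A reader might also infer that Aim 1.2 is biased towards low advancement. That goes too far. The criterion used there is not stated. Titration is led by symptoms whichever criterion applies, so testing at 50% partly reflects the titration rule. The plan also allows for more advancement after the test: "An appointment will be scheduled in the following 2-3 days to return the machine, and to further advance the appliance if needed".

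Finally, the link between the two texts is a reading. STATISTICAL METHODS refers to criteria defined earlier, and the only such definitions visible are in Research Procedures.

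**Conclusion.** The point holds as a defect in how one efficacy proportion can be interpreted, and it should be fixed. It follows from the wording of the rule and the absence of an AHI/RDI floor, and it needs no numerical assumption. It does not show that the trial's efficacy conclusion is wrong, or that Criterion II is unsuitable as a clinical target.

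The size is unknown. The range of 4% to 36% of all participants depends wholly on the assumed baseline mix, night-to-night variation, symptom response, independence and absence of any AHI effect. It shows that the issue could be small or substantial. It is not an estimate for this trial, and its upper end requires 70% of low-baseline participants to meet a strict symptom rule with no AHI effect. The consequence for Aim 1.2 arises only if Criterion II defines success there.

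**What to change.** Keep Criterion II as written and change the reporting:

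- Report Criterion II by baseline AHI/RDI (<15 vs >=15), with the below-5 limb and the below-15-plus-symptoms limb shown separately.
- Cross-tabulate Criterion II with Criterion I in each stratum, and give the AHI/RDI change there. A cut at baseline 15 alone would still pass small falls such as 16 to 14.
- Rest no efficacy claim on the below-15 limb in participants with baseline <15. Judge them on Criterion I and the below-5 limb.
- State which criterion defines success in Aim 1.2. If it is Criterion II, repeat Aim 1.2 without successes who had baseline <15 and qualified only through the below-15 limb.

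The STATISTICAL METHODS text is in the past tense, so label these tables as added if the analysis is already done.

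No new data are needed, because baseline and follow-up AHI/RDI and symptom scores are already collected. The cost is precision: a 60% success rate has an exact 95% interval of 45% to 74% with 30 of 50, and 41% to 77% with 18 of 30. The success rate that can support an efficacy claim may also be lower.

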- Additional parameters will be controlled, including the presence of morning headaches (to be evaluated via questionnaire at baseline and at each follow-up using NRS), waking up during the night to urinate (to be evaluated at baseline and at each follow-up via questionnaire using continuous numeric scale), and the sleep quality (will be assessed at baseline and when performing the home sleep apnea test, using the Pittsburgh Sleep Quality Index (PSQI) questionnaire). Patients subjective perception of improvement will be assessed at each follow up using visual analog scale (to be extracted from Annex 6).
- Incidence of side effects will be assessed at each follow-up session, including subjective increase/decrease salivation (measured via questionnaire using numeric rating scale), increase/decrease teeth mobility, changes in occlusal contacts (measured in habitual occlusion using 0.01 mm occlusal registration strips (ARTUS corporation®) (to be extracted from Annex 6&7).
- Problems related to the appliance will be measured at each follow up session, considering appliance breaks, cracks, deformation, retention changes, wear, discoloration changes and calculus accumulation (to be extracted from Annex 7).

2) Retrospective study: Archival data will be extracted from records of patients that started MAD therapy for OSA at the Orofacial Pain Clinic (University of Kentucky) between 01/01/2010 and 08/17/2021. An active study involving MAD therapy outcomes (protocol #46643; same PI, [name] [name]) includes a consent form for the retrospective participants to collect retrospective data that allows to use the obtained data in future research projects. The data collection process of the previous study is being conducted using RED Cap (CCTS - University of Kentucky), and through that software, we pretend to obtain a report to identify subjects that started MAD therapy and that had a second sleep study performed to assess the effectiveness of the MAD. Data regarding demographic characteristics (age, gender, BMI and OSA diagnosis), sleep parameters (AHI, RDI, minimum and average oxygen saturation), level of advancement of the MAD (%) prior to the second sleep study, and compliance of use will be extracted creating a deidentified "report" (spreadsheet) from the RED Cap database (assigning progressive numbers (starting with M51)).

Attachments

Attach Type	File Name
DataCollection	Annex MP Orthoapnea.docx

Resources

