Aim 1.1 was to assess the efficacy of the NOA® mandibular advancement device. To do this, we had two different criteria for success as defined before. For each of these criteria, we calculated the proportion of patients who “succeeded” vs. “failed.” As exploratory analyses, we used independent samples t-test or chi-square testes (as appropriate) to compare baseline demographic characteristics between those who succeeded and failed for each of the criteria. **Aim 1.2** was to describe the percentage of advancement (%) needed to reach efficacy for the NOA® appliance in the management of obstructive sleep apnea. For this aim, we only examined the data of those who “succeeded” in Aim 1.1. Paired samples t-tests were carried out to detect the possible statistically significant differences in each of the parameters studied before and after receiving the treatment. The sociodemographic characteristics and other variables of interest of the patients included in the prospective and retrospective studies were described (n, mean \pm SD).

Aim 2 was to describe patient compliance to the NOA® device in the management of obstructive sleep apnea. Using the definition of compliance provided above, we computed the proportion of study participants who complied with the NOA® appliance and described the use in terms of nights per week and hours per night (n, mean \pm SD).

Aim 3 was to assess the incidence and prevalence of temporomandibular disorder (TMD) diagnoses, morning headaches, possible sleep bruxism, nighttime voids, sleep quality, side effects, and of problems related to the NOA® appliance during the titration process by using paired samples t-test or chi-square testes (as appropriate) to compare baseline and final values between those who succeeded and failed for each of the criteria.

Mean and standard deviation and other centralization measures were calculated for quantitative variables, frequencies, and percentage values were calculated for categorical variables. The McNemar test was used as a significance test, with which assessed if there were significant changes. Statistical significance was defined by $p < 0.05$. All analyses were conducted using SPSS version 29.

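### Aim 3 compares side effects, appliance problems and new TMD between successes and failures without allowing for follow-up time, although treatment success itself ends follow-up

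*Combined protocol and SAP*

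**What the plan says.** Research Procedures, prospective section, ties the end of follow-up to the outcome: "If the criteria for success is reached, the participation of the patient in the present study will be ended". For the other group, "Therapeutic failure will be established when at 100% of advancement of the device" and the reduction in AHI/RDI is still insufficient. Duration is individual: "The participation in this research will last between seven to sixteen weeks depending on the time for each patient's individual improvement". Visits are frequent: "Follow up sessions will be scheduled every two weeks until maximum therapeutic benefit is achieved".

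The same section gives three routes to the confirmatory sleep test. One is symptom control. The others are reaching "80% of maximum protrusive or is unable to tolerate the advancement".

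Data Collection & Research Materials adds: "Incidence of side effects will be assessed at each follow-up session". Appliance problems follow the same visit schedule. TMD is assessed with the DC/TMD instruments, but no schedule for repeating the examination is given.

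Statistical Methods, Aim 3, covers incidence and prevalence of TMD diagnoses, side effects and appliance problems, together with headache, voids and sleep quality. It names paired t-tests or chi-square tests "to compare baseline and final values between those who succeeded and failed for each of the criteria", and a later paragraph adds McNemar. Nowhere is there a person-time rate, a common assessment time, or an adjustment for weeks of use or level of advancement.

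**The concern.** The variable that defines the two groups also helps to decide how long each patient is observed. A patient who succeeds early leaves. One who does not is advanced further, wears the device for longer and answers more questionnaires. An event scored as ever reported, or one that stays once it appears (new TMD, an occlusal change, a broken appliance), then has more weeks in which to occur and more visits at which to be recorded.

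The plan could therefore report that failures have more side effects or more TMD when the weekly risk is the same in both groups. Objective 3 of the protocol is about TMD, and side effects are part of the device's rationale in the Background, so the contrast is likely to be read as informative.

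**Working it through.** The plan gives no figure for this comparison, so there is none to reproduce. The check asks how often a plain chi-square test would reject when weekly risk is identical in both groups.

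**Inputs from the documents**
- Participation of 7 to 16 weeks (Research Procedures). The largest possible ratio is 16/7 = 2.29.
- Significance at p < 0.05 (Statistical Methods).
- 45 evaluable patients (study population section). Statistical Methods gives 33 instead; that conflict is a separate matter.

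**Assumptions, not in the documents**
- 30 successes and 15 failures.
- A 7-week risk p7 of 10%, 20% or 30%. The Background quotes short-term side-effect incidences of 6% to 86%, so these values are not extreme.
- A constant weekly event rate, equal in both groups.
- Each patient is counted once, as ever or never having the event.

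**Step 1: risk by time.** Weekly rate h = −ln(1 − p7)/7, which gives 0.0151, 0.0319 and 0.0510. Risk by week t = 1 − (1 − p7)^(t/7). At 16 weeks:
- 1 − 0.9^(16/7) = 21.4%, ratio to 7 weeks 2.14
- 1 − 0.8^(16/7) = 40.0%, ratio 2.00
- 1 − 0.7^(16/7) = 55.7%, ratio 1.86

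**Step 2: rejection rate.** Probabilities are summed exactly over all outcomes of Bin(30, success risk) and Bin(15, failure risk), using the uncorrected chi-square test at 0.05.

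| Weeks, successes vs failures | p7 = 10% | p7 = 20% | p7 = 30% |
|---|---|---|---|
| 7 vs 7 | 4% | 5% | 5% |
| 7 vs 16 | 18% | 31% | 39% |
| 7 vs 12 | 10% | 15% | 19% |
| 9 vs 13 | 7% | 11% | 12% |
| 10 vs 12 | 5% | 7% | 6% |

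A continuity correction lowers the 7 vs 16 row to 9–28%. With 33 patients split 22 and 11, that row gives 26% at p7 = 20% and 34% at p7 = 30%.

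**Step 3: per person-week.** With weeks counted to the first event or the end of follow-up at T, expected events per patient are 1 − exp(−hT) and expected weeks at risk are (1 − exp(−hT))/h. Their ratio is h whatever T is, so the rate ratio is 1.0 for every row of the table.

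**Step 4: the alternative reading of Aim 3.** Suppose only status at the final visit is compared, and effects are transient with an assumed mean duration D of 2 to 4 weeks. Prevalence at week t is h/(h + 1/D) × (1 − exp(−(h + 1/D)t)). At p7 = 20% and D = 4 weeks this is 9.7% at week 7 and 11.2% at week 16. Across p7 of 10–30% and D of 2–4 weeks, rejection at 7 vs 16 weeks is 3–5%, so there is no inflation.

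**The case against.** Four objections have force.

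**Aim 3 may not mean ever-events.** It speaks of baseline and final values, and the paired and McNemar tests it names are within-patient. On that reading, transient effects show no inflation (step 4), and the headache, voids and PSQI scores are not incidence outcomes at all. This stands and limits the point to ever-reported or persistent events. It does not remove the point, because Aim 3 names incidence and the success-versus-failure contrast explicitly.

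**Failures are not always followed longer.** A reader might infer that every failure has more time at risk. The documents do not support that. A patient who cannot tolerate advancement goes to the sleep test early, and some successes come only at the last step. The text also does not say whether one or both efficacy criteria end participation, so a patient who leaves on Criterion I could be a short-follow-up failure on Criterion II. Longer observation of failures is a tendency of the design, and time can confound in either direction.

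**The 7 versus 16 week split is the extreme.** It puts every success at the minimum and every failure at the maximum. These are also weeks of participation: the appliance is made to order after impressions, and weeks of wear are not stated.

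**Comparison with other devices.** A reader might infer that the crude incidence is useless against any other device. That goes too far. Objective 3 concerns this device only, the planned retrospective extraction contains no side-effect or TMD data, and risk during titration is a legitimate descriptive quantity for an uncontrolled study.

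**Conclusion.** The point holds in a limited form, as a cheap improvement to a secondary aim. Follow-up length depends on the outcome that defines the groups, and Aim 3 makes no allowance for it. For ever-reported or persistent events, a crude chi-square between successes and failures therefore mixes exposure time with risk.

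The size depends on a gap in follow-up that the documents do not fix. Under the assumptions above, false rejection is 18–39% at the extreme, 10–19% at 7 versus 12 weeks, 7–12% at 9 versus 13 and 5–7% at 10 versus 12. The top figure should not be read as the expected error rate of this trial. Final-visit status of transient effects and the score outcomes are not affected in this way.

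Allowing for time does not make the contrast causal. Failures also reach greater advancement, which the Background links to more side effects.

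**What to change.** In Aim 3:
- Report weeks of device use, counted from delivery and not from enrolment, by success group.
- Report each incident side effect, appliance problem and new TMD as events per person-week of use with an exact Poisson confidence interval, beside the percentage.
- Replace the crude ever-event chi-square between successes and failures. One option is a comparison at an early follow-up visit that all participants attend; since advancement is decided at follow-up visits, the first of these also precedes any difference in advancement. The other is a rate ratio with log person-weeks as offset, labelled associational because of advancement.
- For TMD, state when the examination is repeated and count person-weeks to that examination. Two-weekly Kaplan-Meier curves should not be required: no repeat schedule is given, and exit is driven by the outcome, so censoring is unlikely to be non-informative.

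Separately, Research Procedures builds and tests the device up to 80% of maximum protrusion but defines failure at 100% of device advancement. These passages must be reconciled, because they set when failure is declared and so how long failures are followed.

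The cost is SAP wording, delivery and visit dates, and a small extra table. No new visits or patients are needed. The downside is wide intervals where events are few, and an early-visit comparison sees only early events.
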